AR	Adverse reactions
C&C	Capacity and capability
CAT	Complexity assessment tool
CI	Chief Investigator
CPS	Combined positive score
CR	Complete response
CRF	Case report form
cSCC	Cutaneous squamous cell carcinoma
CTCAE	Common Terminology Criteria for Adverse Events
ctDNA	Circulating tumour DNA
DNA	Deoxyribonucleic acid
ECOG	Eastern Cooperative Oncology Group
EORTC	European Organization for Research and Treatment of Cancer (EORTC)
FFPE	Formalin-fixed paraffin embedded
GCP	Good Clinical Practice
GSTT	Guy's and St Thomas NHS Foundation Trust
HNSCC	Head and neck squamous cell carcinoma
HPV	Human papillomavirus
HTA	Human Tissue Act
KCL	Kings College London
LIPS	Liquid immune profile-based signature
LRBC	Local recurrent breast cancer
MDT	Multidisciplinary team
NA	Not applicable
NASSS	Non-adoption, abandonment, scale-up, spread, and sustainability
NHS	National Health Service
ORR	Objective response rate
OS	Overall survival
PBMC	Peripheral blood mononuclear cells
PD	Progressive disease
PD-L1	Programmed cell death ligand 1
PFS	Progression-free survival
PI	Principal investigator
PR	Partial response
PROM	Patient-reported outcome measure
QLQ	Quality of Life Core Questionnaire
QoL	Quality of life
R&D	Research and Development
RNA	Ribonucleic acid
RT	Radiotherapy
SAE	Serious Adverse Event
SOC	Standard of care
UK	United Kingdom
wIRA	Water-filtered infrared A

4 Summary/Synopsis

Trial Title	Prospective study to assess the real-world implementation of Thermotherapy using wIRA (water-filtered infrared A superficial hyperthermia) in addition to standard of care (SOC) palliative Radiotherapy (RT) in patients with inoperable or incurable cancers	
Short Title	ThermoRad wIRA	
Protocol Version number and Date	Version 2.0, 12 th May 2025	
IRAS Number	327431	
REC Reference	24/SC/0146	
Study Duration	3 years (2 years of recruitment followed by 12 months' follow-up period from the last participant recruited into the study)	
Sponsor name	KCL/GSTT	
Chief Investigator	[name]	
Funder	Dr. med. h.c. Erwin Braun Stiftung Foundation, Switzerland	
Medical condition or disease under investigation	
Inoperable or incurable cancers with at least one lesion suitable for wIRA treatment, consisting of different cohorts of patients:
 
 1) recurrent/metastatic head and neck squamous cell carcinoma (HNSCC) 2) cutaneous squamous cell carcinoma (cSCC) not suitable for radical treatment 3) locally recurrent breast cancer (LRBC) 	
	Objectives	Endpoints
Primary	To assess the real-world implementation of superficial hyperthermia using CE marked water-filtered infrared A (wIRA) in addition to palliative SOC radiotherapy	
 1. Quantitative: the total number and types of cancer patients successfully treated with the combination of superficial hyperthermia and palliative radiotherapy. 2. Descriptive: to evaluate the real-world implementation by the NASSS (non-adoption, abandonment, scale-up, spread, and sustainability) framework using NASSS-CAT (complexity assessment tool)
Secondary	1. To assess the best objective response rate (ORR) of the lesion(s) treated with combination of superficial hyperthermia with palliative radiotherapy	
 1. Best ORR: Defined as the proportion of patients achieving either a Complete Response (CR) or a Partial Response (PR). Complete Response (CR): Disappearance of all target lesions.

		Partial Response (PR): $\geq 30\%$ decrease in the sum of diameters of target lesions, taking as reference the baseline sum diameters.
	2. To determine the tolerability and safety profile of superficial hyperthermia in patients receiving SOC palliative radiotherapy	2. Local serious adverse events (SAEs) will be assessed by Common Terminology Criteria for Adverse Events (CTCAE) version 5.0.
	3. To evaluate the median local and global progression-free survival (PFS) and median overall survival (OS) of patients at 12 months after the last patient is recruited	
3. Patients not experiencing an event (progression or death) will be censored at the time of the final analysis at the date last known to be alive and progression-free.
 
Local: refer to the lesions treated by radiotherapy +/- superficial hyperthermia.
 
Global: local and distant (non-treated lesions)
 
PFS: Defined as the time from baseline to the first documented progressive disease (PD) or death from any cause, whichever occurs first.
 
Progressive disease (PD): At least a 20% increase in the sum of diameters of target lesions or development of new lesions, with the date of progression recorded by a clinician in the patient's hospital records.
 
OS: The time from the start of treatment to death from any cause.

	4. To assess the median duration of objective response and locoregional control rates of the treated lesion(s) at 6 and 12 months	
4. Duration of Objective Response: Defined as the time from the first documented Complete Response (CR) or Partial Response (PR) to disease progression or metastasis.
 
Locoregional Control Rate: The proportion of patients whose primary tumour site remains free from progression.

	
5. To assess patient-reported outcomes measures (PROMs)
	
5. PROMs assessment using the European Organization for Research and Treatment of Cancer (EORTC) Quality of Life Core Questionnaire (QLQ-C30), European Organisation for Research and Treatment of Cancer Quality of Life Questionnaire Head and Neck Module (QLQ-H&N43) (for HNSCC cohort)
 
PROMs will be collected at baseline, during treatment (after the 3rd fraction of radiotherapy), 6 weeks post-treatment, 12-weeks post-treatment.

	
6. To assess the differences in the efficacy between the lesion(s) treated with radiotherapy with hyperthermia with the lesion(s) treated with radiotherapy alone in those patients with at least 1 additional lesion that is not suitable for treatment with hyperthermia at 6 and 12 months
	
6. Percentage of best ORR, duration of response and disease control rates at 6 and 12 months in the lesion(s) treated with hyperthermia and radiotherapy versus lesion(s) treated with radiotherapy alone.

	
7. To compare clinical outcome of patients treated with superficial hyperthermia in addition to SOC radiotherapy with historical control
	
7. Retrospectively collect data for historical cohort of similar cancer patients treated with SOC radiotherapy alone

Number of Subjects/Patients	
 Up to 60 patients treated with superficial hyperthermia using water-filtered infrared hyperthermia (wIRA) hydrosun® TWH1500 treatment 	
Patient cohorts	
1) HNSCC
 
 i) Inoperable/incurable or recurrent/metastatic HNSCC with no previous radiotherapy treatment ii) Inoperable/incurable or recurrent/metastatic HNSCC with previous radiotherapy treatment (re-irradiation) 
2) cSCC
 
 i) Inoperable/incurable or recurrent/metastatic cSCC with no previous radiotherapy treatment ii) Inoperable/incurable or recurrent/metastatic cSCC with previous radiotherapy treatment (re-irradiation) 
3) LRBC
 
locally recurrent breast cancer with previous radiotherapy treatment (re-irradiation)
	

Study Type	Interventional study to implement superficial hyperthermia using wIRA machine in the real-world setting
Study endpoints	The end of the study definition is 12 months from the last participant recruited into the study after the 24-month recruitment period.
Main Inclusion Criteria	
 1. Patient with histologically confirmed incurable or inoperable cancers with disease [at least one superficial lesion(s) or lymph node(s)] suitable for hydrosun® TWH1500 treatment 2. Patient undergoing standard of care palliative radiotherapy (suitable with the pre-specified dose and fractionation in the protocol) 3. Aged ≥18 years old 4. Eastern Cooperative Oncology Group (ECOG) performance status 0 to 2 5. Patient with capacity to consent
Statistical Methodology and Analysis	This is a prospective study aiming to implement superficial hyperthermia using wIRA machine in the real-world setting and to recruit 15-20 patients in each disease cohort above (total = up to 60), which is the realistic target for two years.
Human Tissue and blood Samples (if applicable)	Peripheral bloods will be collected, and archival tissues will be requested to assess the peripheral and tissue immune markers. Other biological samples such as saliva, oral swab, urine, and stool samples may be collected for future translational research.
Data collected/storage (if applicable)	Patients' demographics, smoking and alcohol history, tumour characteristics, treatment details and responses, recurrences and survivals will be obtained from clinical record and recorded on paper Case Report Forms (CRFs).

5 Introduction

Head and neck squamous cell carcinoma (HNSCC) is the sixth most common cancer worldwide and there are around 12 000 new cases in the UK each year (1). The most common causative agents include alcohol intake and smoking; however human papillomavirus (HPV) infection accounts for an increasing incidence of oropharyngeal cancer (2, 3). Patients presented with local disease can be offered treatment with surgery and/or radiotherapy with or without concurrent chemotherapy. Despite intensive treatment, 5-year survival rate remains poor, at approximately 50% for patients with high-risk features (HPV negative tumours and heavy smoking history) (4). Concurrent platinum chemotherapy with radical radiotherapy has been shown to increase survival in locally advanced HNSCC, but no survival benefit and poor tolerability was seen in those patients over 70 years old (5, 6), resulting in these patients being offered radiotherapy alone (with poorer outcomes). In addition, patients with locally advanced HNSCC who are older with co-morbidities are not fit or suitable for curative radical treatments, consisting of either primary surgery followed by adjuvant postoperative radiotherapy +/- chemotherapy or primary radiotherapy +/- concurrent chemotherapy. These patients

often end up receiving palliative radiotherapy alone. The focus of treatment for these patients is palliation to improve symptoms as well as to extend their life expectancy. Palliative radiotherapy treatment has been used successfully for both local control and palliation.

More recently these HNSCC patients are also treated with palliative immunotherapy if they are deemed fit to receive this treatment since the approval of pembrolizumab monotherapy in November 2020 in the UK as a result of the KEYNOTE-048 trial (7). In this study, it was shown that pembrolizumab monotherapy extended overall survival (OS) over the first-line chemotherapy in patients with HNSCC tumours with a programmed cell death ligand 1 (PD-L1) combined positive score (CPS) of $\geq 20\%$ (HR = 0.61; $p=0.007$) and $\geq 1\%$ (HR = 0.78; $p=0.086$) with favourable safety (7). This has resulted in the approval of pembrolizumab monotherapy for patients with HNSCC with CPS score $\geq 1\%$.

In addition to HNSCC, most patients with cutaneous SCC (cSCC) tend to be older with co-morbidities and many of them are not suitable or fit to undergo a course of curative treatment with a combination of surgery and/or radiotherapy. Cemiplimab is approved for use in patients with metastatic or locally advanced unresectable cSCC after a previous publication showed an objective response rate (ORR) of nearly 50% in these patients (8). In patients with locally advanced cutaneous SCC (cSCC) not suitable for curative surgery or radical radiotherapy, cemiplimab showed an antitumour activity with an objective response rate of 44% (of which complete response, CR, was 13%) and an acceptable safety profile (9). Thus, patients with incurable or recurrent cSCC not able to have curative treatment are often given palliative radiotherapy and/or cemiplimab since its approval in the UK.

The use of heat treatment in the management of malignant tumours has a long history and can be dated back to the ancient Greeks (10). Hyperthermia treatment involves the use of specific machines to apply heat, aiming to induce mild tumour heating up to a maximum temperature of 45°C (11, 12). It can further subdivide into three main categories including local, locoregional, and whole-body hyperthermia. Local heating is described as the process of heating the tumour volume, with no (or minimal) heating of normal surrounding tissue (11). It is widely evident that hyperthermia is a radiosensitiser through several mechanisms including reduction of hypoxia, increased vascular supply and inhibition of DNA repair (13-15). Moreover, it enhances the immune system and the synergistic effect with radiotherapy can lead to immunogenic cell death (16, 17).

Several technologies have been employed for the development of clinically approved superficial heating devices including microwave antenna, external infrared sources, ultrasound transducers and radiofrequency electrodes (11). The Hydrosun system (Hydrosun medizintechnik GmbH) uses water-filtered infra-red-A (wIRA) superficial hyperthermia technology to deliver contact free heating to large tumour areas (18). Despite the use of hyperthermia treatment in combination with other cancer

treatments such as radiotherapy and chemotherapy at many cancer centres across the world, its use has not been established in NHS settings. The main difficulties in introducing its use into routine clinical practise is the lack of expertise in its use as well as the lack of availability of clinically approved hyperthermia machines at any UK cancer centre. Guys Cancer Centre is the first centre nationally to introduce a CE marked hyperthermia machine (hydrosun®-TWH1500) for patient use in the NHS.

Patients presented with inoperable/recurrent disease usually have limited prognosis and any associated symptoms such as pain, discharge, infection, and bleeding significantly affect their quality of life. Several publications support the clinical use of hyperthermia with palliative radiotherapy in multiple tumour types (19). Datta et.al provides a summary of the clinical outcomes of 38 clinical trials across various tumour sites including breast, head and neck and skin melanoma comparing radiotherapy (1717 patients) versus thermoradiotherapy (1761 patients) and reported an overall clinical response of 54.9% in thermoradiotherapy groups vs 38.9% in the radiotherapy alone group (odds ratio: 2.3, 95% confidence interval 1.95–2.72, $p < 0.001$) (19). In a randomised phase 3 trial of patients with superficial measurable tumours treated with either radiotherapy alone or radiotherapy followed immediately by hyperthermia (42.5 degrees C, 45-60 min), a better CR rate was observed with a combination of radiotherapy and heat (62 and 67%) compared with irradiation alone (40 and 0%) in tumours less than 3 cm in diameter in the breast, trunk, and extremities despite no difference in overall CR between the two arms (20).

In head and neck cancer, a systematic review and meta-analysis comparing the efficacy of hyperthermia plus radiotherapy over radiotherapy alone showed an overall CR of 62.5% in the combination treatment versus 39.6% in the radiotherapy alone group (21). Moreover, a systematic review investigating the role of hyperthermia in the treatment of local recurrent breast cancer (LRBC) showed that the combination of hyperthermia with radiotherapy achieved a complete response rate of 60.2% compared to 38.1% for radiotherapy alone (22). However, most of the previous evidence is based on older hyperthermia and radiotherapy techniques, which have been disregarded by many oncologists as non-comparable to current standard of care.

The wIRA superficial hyperthermia system have been used in the EU and Switzerland for several years, which is proposed here, to treat patients with superficial tumours although most experience has been on locally recurrent breast cancers (LRBC) who had been previously and/or heavily irradiated. In a retrospective study of 73 LRBC patients, a CR rate of 61% was achieved in those with macroscopic disease (n=64) after being treated with re-irradiation 4 Gy per fraction per week for 5 weeks (4Gy x 5) with hyperthermia (18). They have further published another cohort of 201 patients treated with re-irradiation with hyperthermia in 2020 with similar efficacy and acceptable toxicities

(23). However, as most evidence has come from LRBC, there is uncertainty whether this real-world evidence is applicable to cutaneous SCC or HNSCC. In addition, there is uncertainty whether the weekly dose of 4Gy per week in combination with superficial hyperthermia using wIRA would be suitable for HNSCC or cSCC patients since the tumours may be more rapidly growing and this fractionation is not normally used in the standard of care. Furthermore, most of these patients also receive immunotherapy after palliative radiotherapy as part of the standard of care and there is uncertainty how this affects these patients receiving superficial hyperthermia and SOC palliative radiotherapy.

Through this prospective study, we hope to demonstrate the successful implementation of CE marked wIRA superficial hyperthermia in addition to SOC palliative radiation or re-irradiation in patients with inoperable or incurable cancers.

6. Aims and objectives:

- **Overall aim:**

This is a prospective study to assess the real-world implementation of superficial hyperthermia (wIRA) in addition to SOC palliative radiotherapy in cancer patients.

- **Patient's cohorts:**

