1. HNSCC

- i. Inoperable/incurable locally advanced or recurrent/metastatic HNSCC with no previous radiotherapy treatment
- ii. Inoperable/incurable locally advanced or recurrent/metastatic HNSCC with previous radiotherapy treatment (re-irradiation)

2. cSCC in the head and neck region

- i) Inoperable/incurable locally advanced or recurrent/metastatic cSCC with no previous radiotherapy treatment
- ii) Inoperable/incurable locally advanced or recurrent/metastatic cSCC with previous radiotherapy treatment (re-irradiation)

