3. LRBC

- i) Locally recurrent breast cancer with previous radiotherapy treatment (re-irradiation)

- **Primary objective:**

1. To assess the real-world implementation of superficial hyperthermia [using CE marked water-filtered infrared A (wIRA) machine] in addition to palliative SOC radiotherapy

- **Secondary objectives:**

1. To assess the best objective response rate (ORR) of the lesions treated with the combination of superficial hyperthermia (wIRA) and palliative radiotherapy
2. To determine the tolerability and safety profile of the combination treatment of superficial hyperthermia (wIRA) and palliative radiotherapy
3. To evaluate the median progression-free survival (PFS) and overall survival (OS) of patients
4. To assess the median duration of objective response and locoregional control rates at 6 and 12 months
5. To assess patient-reported outcome measures (PROMs) and quality of life (QoL) of patients using the European Organization for Research and Treatment of Cancer (EORTC) Quality of Life Core Questionnaire (QLQ-C30) and head and neck module (QLQ-H&N35)
6. To assess the differences in the efficacy between the lesion(s) treated with radiotherapy with hyperthermia with the lesion(s) treated with radiotherapy alone in those patients with at least 1 additional lesion that is not suitable for treatment with hyperthermia
7. To compare clinical outcome of patients treated with combination of superficial hyperthermia and radiotherapy who may or may not undergo subsequent immunotherapy with the retrospective data of historical cohorts

- **Exploratory objectives/translational research:**

Collection of samples such as archival tumour sample, fresh tumour biopsy/resected sample when available, blood (PBMC), and saliva, for translational research (see below).

- **Table 1: Objectives and endpoints**

	Objectives	Endpoints
--	-------------------	------------------

Primary	To assess the real-world implementation of superficial hyperthermia using CE marked water-filtered infrared A (wIRA) in addition to palliative SOC radiotherapy as part of their standard of care (SOC)	
1. Quantitative: the total number and types of cancer patients successfully treated with the combination of superficial hyperthermia and palliative radiotherapy.
 
2. Descriptive: to evaluate the real-world implementation by the NASSS (non-adoption, abandonment, and challenges to scale-up, spread, and sustainability) framework using NASSS-CAT (complexity assessment tool) ⁵

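### Secondary endpoint 4 scores locoregional control at the primary tumour site, but its objective asks about the treated lesion(s), which need not be there

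*Protocol*

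**What the plan says.** Secondary objective 4 reads the same in the Synopsis (section 4) and in Table 1 (section 6): "To assess the median duration of objective response and locoregional control rates of the treated lesion(s) at 6 and 12 months". In both tables the endpoint beside it is "Locoregional Control Rate: The proportion of patients whose primary tumour site remains free from progression".

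The list of secondary objectives in section 6 gives a shorter form that names no site: "To assess the median duration of objective response and locoregional control rates at 6 and 12 months".

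For secondary endpoint 3 the protocol says what local means: "Local: refer to the lesions treated by radiotherapy +/- superficial hyperthermia".

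On who may be treated, the inclusion criteria (Synopsis and section 8) ask for "at least one superficial lesion(s) or lymph node(s") suitable for the device. The cohorts in section 6 include "Inoperable/incurable locally advanced or recurrent/metastatic HNSCC with previous radiotherapy treatment (re-irradiation"), with a parallel entry for cSCC. The Synopsis plans "to recruit 15-20 patients in each disease cohort above (total = up to 60").

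**The concern.** An endpoint should measure what its objective asks. Here the objective concerns the lesions that received treatment, while the endpoint concerns the anatomical site of the primary tumour. The two agree when the only treated lesion is at the primary site. They can disagree when the treated lesion is a lymph node or another lesion elsewhere, which the eligibility criteria allow.

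At stake is the meaning of the reported control rate. Someone extracting data from the notes and following the text would score the primary even where it was not treated. The resulting rate would mix control of treated disease with the behaviour of disease that the study treatment never reached.

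**Working it through.** The protocol reports no figure that depends on this definition, so there is nothing to reproduce. The check compares the texts and then works out the weight of one misclassified patient.

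**Step 1: the site each text names.**

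| Place | Site assessed |
|---|---|
| Objective 4, Synopsis and Table 1 | treated lesion(s) |
| Endpoint 4, Synopsis and Table 1 | primary tumour site |
| Objective 4, section 6 list | none named |
| Endpoint 3, meaning of local | lesions treated by radiotherapy, with or without hyperthermia |

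Endpoint 4 stands alone. Nothing in the protocol equates the primary tumour site with the treated lesion(s). The definition also leaves out the regional part of locoregional: read literally, a treated regional node does not count.

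**Step 2: whether the sites can differ in an eligible patient.** Yes. A suitable superficial lesion or lymph node is enough, disease at the primary site is not required, and two cohorts admit recurrent or metastatic disease. The argument does not need the LRBC cohort.

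**Step 3: how such a patient is classified.**

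| Treated lesion (away from primary) | Primary site (untreated) | Under objective 4 | Under endpoint 4 |
|---|---|---|---|
| progresses | clear | failure | controlled |
| controlled | progresses | controlled | failure |
| controlled | clear | controlled | controlled |
| progresses | progresses | failure | failure |

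The first two rows are discordant, and they err in opposite directions.

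**Step 4: size.** Let *a* be the number of patients in the first row, *b* the number in the second, and *N* the number analysed. The error in the rate is (*a* − *b*)/*N*. It cannot exceed, in absolute value, the share of patients treated away from the primary. The protocol gives neither *a*, nor *b*, nor that share, so the error itself cannot be computed. The weight of one discordant patient follows from the recruitment targets:

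- all cohorts, *N* = 60: 1/60 = 1.7 percentage points
- one cohort, *N* = 20: 1/20 = 5.0 points
- one cohort, *N* = 15: 1/15 = 6.7 points

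**The case against.** **Treated-lesion outcome is captured elsewhere.** This stands in part. Local PFS is tied to the treated lesions, and secondary endpoint 6 asks for disease control at 6 and 12 months by lesion group. Neither replaces endpoint 4. PFS counts death and new lesions as events, and endpoint 6 covers only patients who also have a lesion unsuitable for hyperthermia.

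**The sponsor could change the objective instead.** The section 6 list names no site and is compatible with the endpoint as written. That would remove the contradiction. However, both tables specify the treated lesion(s), and the protocol's meaning of local points the same way, so changing the endpoint is the smaller and more useful repair.

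**The rate is descriptive.** Section 14 states that no formal power calculation was done, and nothing shown tests a hypothesis on this rate. This limits the weight of the point but does not make the definition answer its objective. Nor is it a detail left for an analysis plan: the protocol fixes the definition twice.

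**A separate request to split control by treatment received.** This is not needed here, since endpoint 6 already compares lesions given hyperthermia plus radiotherapy with lesions given radiotherapy alone.

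**A stronger reading about duration of response.** Endpoint 4 defines duration as "Defined as the time from the first documented Complete Response (CR) or Partial Response (PR) to disease progression or metastasis". A reader might infer that a distant metastasis would end response in both lesion groups of endpoint 6 on the same date and hide any difference. The text does not establish this. Endpoint 6 asks for duration in the lesion(s) treated each way and does not say that the endpoint 4 definition applies. A lesion-level reading is open, so this merits at most a clarification.

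**Conclusion.** The mismatch is real and appears in both objective and endpoint tables. As written, endpoint 4 does not answer objective 4 for patients treated away from the primary site, and the direction of the error cannot be predicted. Each discordant patient is worth 1.7 points overall, or 5.0 to 6.7 points within a cohort, assuming the recruitment targets are met and every patient is evaluable.

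A reader might go on to assume a case mix and quote a total bias of so many points. The protocol gives no share of patients treated off the primary and no control rates at either site, so any such total would rest wholly on the assumption.

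The point should be fixed, but its reach is limited to the control rate in one secondary endpoint. The primary endpoints and the criteria in section 9 for continuing beyond two years are untouched.

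**What to change.** 1. In secondary endpoint 4, in both the Synopsis and Table 1, replace the primary tumour site with the treated lesion(s), defined as local already is for endpoint 3: lesions treated by radiotherapy, with or without superficial hyperthermia.
2. In the section 6 list, add to objective 4 that it concerns the treated lesion(s), so that all three statements agree.
3. Optional: state that duration of response in endpoint 6 is measured on the lesion group concerned.

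The cost is wording in three places and a record, for each patient, of which lesions were treated. Under section 13, responses and progression are taken from the clinical record, and the schedule of events lists no tumour measurement. The change is therefore best made before outcomes are extracted, with a check that the notes identify the treated lesions well enough to score them.
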